#### **Design: Retrospective Comparison and Prospective Cohort Study**

Four groups of patients will be utilized in this study as follows:

**A: Hospital Group:** this group will receive both doses of TXA according to the draft protocol upon arrival to the participating trauma center. No TXA will be given in the field to this patient grouping. 200 patients shall be enrolled in this group in a prospective observational study format.

**B: Air Transport Group:** This group will receive the first dose of TXA according to the draft protocol on scene or during the flight by a licensed flight RN or licensed flight physician. The second dose of TXA will be administered upon arrival at the participating trauma center. 200 patients shall be enrolled in this group in a prospective observational study format.

**C: Paramedic Group:** These patients will receive their first dose of TXA according to the draft protocol in the field by licensed paramedics from participating agencies. The second dose of TXA will be

administered upon arrival at the participating trauma centers. 200 patients shall be enrolled in this group in a prospective observational study format.

**D: Control Group:** 200 patients, transported by ambulance or by air, with similar injury severity and hemodynamics shall be randomly chosen from the previous five years of the trauma registry at the participating trauma center. These patients shall then be compared to Group A, B and C noted above in a retrospective comparison.

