### **Comparisons:**

Groups A, B and C shall be compared to each other in the following format.

1. Hospital/TXA vs. Air Transport/TXA
2. Hospital/TXA vs. Paramedic/TXA
3. Air Transport/TXA vs. Paramedic/TXA
4. Hospital vs. Control Group to validate results of the CRASH-2 Study

All patients receiving TXA should utilize the same inclusion criteria no matter what group they fall into (excluding the control group) to allow for accurate and consistent comparison. All patients in the control group should meet the same inclusion criteria as the patients who received TXA in groups A, B and C.

Patients who fulfill the inclusion criteria will be administered TXA at the participating trauma center or in the field by trained Paramedics, RNs or Flight Physicians from the participating agencies according to the study protocol. The first dose of the TXA (1gm over 10 minutes intravenous or interosseous drip) shall be administered as soon as possible by the hospital or the participating responder teams. A red colored wristband labeled “TXA” attached to their right wrist and/or TXA written on their chest will identify patients who received TXA. Subsequently, upon arrival at the participating trauma center the patients who received TXA will be identified and re-assessed by the trauma team members for hemorrhagic shock. If the patient still meets inclusion criteria, the TXA will be continued at the participating trauma center (1gm over 8 hours intravenous infusion). Patients that meet the inclusion criteria and were not given TXA because they were brought to the emergency department by agencies other than participating agencies will be assigned to the Group A. Administration of TXA is not anticipated to delay patient transport to participating trauma centers. Currently, TXA is part of the mass transfusion protocol at ARMC for patients in traumatic hemorrhagic shock.

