**Inclusion criteria:**

The hospital and prehospital use of TXA should be considered for all trauma patients that meet **any** of the following criteria:

- Blunt or penetrating trauma with signs and symptoms of hemorrhagic shock.
- Systolic blood pressure of less than 90 mmHg at scene of injury, during air or/and ground medical transport, or on arrival to designated trauma centers
- Any Sustained Blunt or Penetrating injury within 3 hours
- Patients who are considered to be high risk for significant hemorrhage
  - Estimated blood loss of 500 milliliters in the field accompanied with HR >120.
  - Bleeding not controlled by direct pressure or tourniquet.
  - Major amputation of any extremity above the wrists and above the ankles.

[figure not shown]

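### Transporting agency shapes entry to Groups A, B and C but not the draw of control Group D, and it is neither recorded nor adjusted for

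*Combined protocol and SAP*

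**What the plan says.** All places are in the combined protocol and SAP.

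- **Group A (Design).** Both doses are given at the trauma center, and "No TXA will be given in the field to this patient grouping". Agency is not part of this definition. Comparisons adds one route into the group: eligible patients "brought to the emergency department by agencies other than participating agencies will be assigned to the Group A". The Inclusion criteria give another, since low systolic pressure may first be found "or on arrival to designated trauma centers", whichever agency brought the patient.
- **Groups B and C.** Group C receives its first dose "in the field by licensed paramedics from participating agencies". Comparisons covers the flight crews too: field dosing is done "in the field by trained Paramedics, RNs or Flight Physicians from the participating agencies". Both groups therefore come from participating agencies.
- **Group D (Design).** This is a trauma-registry sample of 200, made up of those "transported by ambulance or by air, with similar injury severity and hemodynamics shall be randomly chosen from the previous five years". Comparisons requires them to meet the TXA groups' inclusion criteria. Neither section mentions agency.
- **Comparisons with D.** Design says "These patients shall then be compared to Group A, B and C noted above in a retrospective comparison". The numbered list under Comparisons contains only one such contrast, item 4 (Hospital vs Control).
- **Data and analysis.** Data collection and Analysis Measures do not list transporting agency. Statistical analysis names a t test, regression and chi-square, with no covariates.

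**The concern.** Agency participation helps decide which TXA group a patient can enter, but it plays no part in choosing the controls. If patients of participating and non-participating agencies differ in baseline risk, for instance through distance, injury mix or crew practice, a contrast with D can show a mortality difference when TXA has no effect. Knowing whether transport was by air or ground does not identify the agency, so stratifying by mode would not remove this.

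Item 4 is meant to validate CRASH-2, for which the Background cites a 1.5-point reduction in 28-day mortality. Even a modest bias matters on that scale. Larger enrolment would not shrink it. If agency is never collected, it cannot be examined or corrected afterwards.

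**Working it through.** The plan states no figure on this point, so there is none to reproduce. Everything below except the 1.5-point benchmark and the 200 per group is an assumption.

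**Inputs**
- s: share of eligible patients brought by participating agencies, taken as the same in the registry years and the study period (stable agency mix).
- g: fraction of those patients dosed in the field, who go to B or C.
- d: mortality of participating-agency patients minus that of the others, at equal treatment and after any balancing on severity. Its sign is unknown.

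**Step 1: participating share in each group.** Of all eligible patients, s(1−g) are participating but undosed in the field and 1−s are non-participating. Together they form Group A, a fraction 1−sg of the total.
- A: s(1−g)/(1−sg)
- B and C: 1
- D: s

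**Step 2: is A's share below D's?** s − s(1−g)/(1−sg) = sg(1−s)/(1−sg). For 0 < s < 1 this is positive whenever g > 0. It is 0 at g = 0 and reaches s at g = 1.

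**Step 3: bias with no TXA effect.**
- A − D: −[sg(1−s)/(1−sg)]·d, at most s·d in size
- B − D or C − D: +(1−s)·d, whatever g is
- A − B or A − C: −[(1−s)/(1−sg)]·d

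The A − D bias is sg times the A − C bias, so it is always the smaller of the two.

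**Step 4: illustration with s = 0.5, g = 0.8, d = 5 points.**
- A's participating share: 0.5 × 0.2 / (1 − 0.4) = 0.167, against 0.5 in D
- A − D: (0.167 − 0.5) × 5 = −1.7 points; ceiling 0.5 × 5 = 2.5
- C − D: (1 − 0.5) × 5 = +2.5 points
- A − C: (0.167 − 1) × 5 = −4.2 points

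**Step 5: range.** Absolute bias in points; A vs D at g = 0.8, with the g = 1 ceiling s·d in brackets.

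| s | d | A vs D | B or C vs D |
|---|---|---|---|
| 0.3 | 1 | 0.2 (0.3) | 0.7 |
| 0.3 | 3 | 0.7 (0.9) | 2.1 |
| 0.3 | 5 | 1.1 (1.5) | 3.5 |
| 0.5 | 1 | 0.3 (0.5) | 0.5 |
| 0.5 | 3 | 1.0 (1.5) | 1.5 |
| 0.5 | 5 | 1.7 (2.5) | 2.5 |
| 0.7 | 1 | 0.4 (0.7) | 0.3 |
| 0.7 | 3 | 1.1 (2.1) | 0.9 |
| 0.7 | 5 | 1.9 (3.5) | 1.5 |

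At s = 0.5 and g = 0.8, the A vs D bias equals the cited 1.5 points when d = 1.5 / 0.333 = 4.5 points.

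**Step 6: scale against sampling error.** At an assumed 20% mortality, the 95% half-width with 200 per group is 1.96 × √(2 × 0.2 × 0.8 / 200) = 7.8 points.

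**The case against.** **Group A is not defined by agency.** A reader might infer from the assignment rule that A consists only of non-participating-agency patients. The text does not say so: Design sets no agency condition, and patients may first qualify on arrival. If a is the non-participating share of A, the A vs D bias is ((1−a)−s)·d, which vanishes when the two mixes agree, for example at a = s = 0.5. This stands to the extent that s·d is a ceiling, not an estimate. The cancellation does not survive a stable agency mix, because Step 2 then requires g = 0, meaning no field dosing and no Group B or C. If the mix shifted between the registry years and the study, the size and sign could differ, and the documents do not settle that.

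**The gap d is assumed and partly controlled.** This also stands. No section reports a mortality difference between agencies. D must resemble the TXA patients on severity and hemodynamics and meet the same inclusion criteria. Mechanism, area of injury and time from EMS encounter to the emergency department are collected. At d = 1 the A vs D bias is below the benchmark throughout the table. However, no matching method, tolerance or covariate is given, and none of these items identifies the agency.

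**The large figures are tempting.** Setting s = 0.7 and d = 8 gives 0.7 × 8 = 5.6 points for A vs D. That needs A to be wholly non-participating and a gap that nothing in the documents supports.

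**Not every contrast with D is firmly planned.** B and C vs D rest on one sentence in Design, and the numbered list has only A vs D. Comparisons 1 and 2 are the more exposed contrasts. Both remarks are correct.

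**Giving A only non-participating controls would mismatch it the other way.** In the Step 4 example the bias would be 0.167 × 5 = 0.8 points, with opposite sign. This stands and shapes the fix.

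**Conclusion.** The structural imbalance follows from the text. B and C come only from participating agencies, A is enriched for the others, and D is drawn without regard to agency. No agency item or adjustment is planned. Under a stable agency mix, any residual gap d biases A vs D by at most s·d, and biases B or C vs D, if those are done, by (1−s)·d in the opposite direction.

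The size is unknown. The illustrative 1.7 points is similar to the effect that item 4 is meant to validate, but well inside the 7.8-point half-width. It would distort the estimate without being visible, and would seldom decide significance by itself. The result assumes that field dosing occurs, that all other eligible patients enter A, and that d is the same for dosed and undosed participating-agency patients. The documents do not establish a direction, a 5.6-point bias, or that D was drawn from every agency; they state only that no restriction applies.

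**What to change.** 1. Add transporting agency to Data collection for all four groups, coded as participating or not. For D, code it from registry history by the agency's present status.
2. For A vs D, match the D draw to A's observed agency mix, or name agency participation as a regression covariate. Do not limit A's controls to non-participating agencies.
3. Reconcile Design with the numbered list on whether B and C are compared with D. If they are, use D patients brought by now-participating agencies by the same transport mode, and confirm that these patients had no field TXA.
4. State that comparisons 1 and 2 carry more of the agency difference than A vs D, and report them by agency participation where A contains both kinds. Participating-agency patients in A were not dosed in the field, so they remain a selected group and this should be said.

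**Cost.** One registry field, which must be confirmed as available for the past five years; no section says that it is. Intervals widen where D is restricted. With 100 controls against 200 at 20% mortality, the half-width is 1.96 × √(0.16/200 + 0.16/100) = 9.6 points, against 7.8. Drawing more registry records would limit that loss.

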**Inclusion criteria:**

The hospital and prehospital use of TXA should be considered for all trauma patients that meet **any** of the following criteria:

- Blunt or penetrating trauma with signs and symptoms of hemorrhagic shock.
- Systolic blood pressure of less than 90 mmHg at scene of injury, during air or/and ground medical transport, or on arrival to designated trauma centers
- Any Sustained Blunt or Penetrating injury within 3 hours
- Patients who are considered to be high risk for significant hemorrhage
  - Estimated blood loss of 500 milliliters in the field accompanied with HR >120.
  - Bleeding not controlled by direct pressure or tourniquet.
  - Major amputation of any extremity above the wrists and above the ankles.

[figure not shown]

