**Title: Tranexamic Acid in Prehospital and In Hospital Civilian Trauma Care in Antifibrinolytic Therapy Study**

**NCT#**

**Date: March 7, 2018**

## **Research Project**

**Title:** The role of pre-hospital Tranexamic Acid (TXA) to improve traumatic hemorrhagic shock outcomes.

Early Prehospital Antifibrinolytic Therapy (EPAT) is a prospective observational and a retrospective comparison cohort study of early administration of TXA. TXA will be administered in the hospital and prehospital setting to trauma patients with associated indices of hemorrhagic shock. The efficacy of hospital and prehospital TXA will be assessed via its effect on mortality, total and types of blood products used, total estimated blood loss and the occurrence of adverse thromboembolic events.

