**Purpose:**

To determine if pre-hospital administration of TXA in trauma patients with signs of hemorrhagic shock provides for a statistically significant decrease in mortality, total blood product usage and total estimated blood loss, without a significant increase in thromboembolic complications.

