**Exclusion criteria:**

- Any patient under 18 years of age.
- Any patient with an active thromboembolic event (within the last 24 hours) – i.e. active stroke, myocardial infarction or pulmonary embolism.
- Any patient with a hypersensitivity or anaphylactic reaction to TXA.
- Any patient more than three-hour post injury.
- Traumatic arrest with > 5 minutes CPR without return of vital signs
- Penetrating cranial injury
- Traumatic brain injury with brain matter exposed
- Isolated drowning or hanging victims
- Documented cervical cord injury with motor deficit

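### The inclusion list is joined by *any*, so a recent blunt or penetrating injury alone makes a patient eligible, which contradicts the hemorrhagic-shock population named in the Purpose

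*Combined protocol and SAP*

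**What the plan says.** The Inclusion criteria section opens by saying that TXA "should be considered for all trauma patients that meet any of the following criteria", with the word *any* in bold. One of the items is "Any Sustained Blunt or Penetrating injury within 3 hours". It is a separate item and carries no condition on bleeding, blood pressure or shock.

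The Research Project section describes the patients as "trauma patients with associated indices of hemorrhagic shock". The Purpose section concerns "pre-hospital administration of TXA in trauma patients with signs of hemorrhagic shock". The Exclusion criteria rule out "Any patient more than three-hour post injury".

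The Comparisons section gives the list its force in three ways:
- Patients who fulfil the criteria are to be given TXA.
- Patients treated in the field are re-assessed for hemorrhagic shock on arrival, and the second dose follows if they continue to meet the criteria.
- "All patients in the control group should meet the same inclusion criteria as the patients who received TXA in groups A, B and C".

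The Design section adds that Group D is to resemble the treated groups in severity of injury and hemodynamic state.

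**The concern.** The list defines a wider population than the question the study asks. A patient with a recent injury and no bleeding satisfies it, although TXA has no hemorrhage to act on in that patient. Any such patients would weaken the apparent effect on mortality, transfusion and blood loss. They would also carry whatever thromboembolic risk the drug has.

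The groups could also come to differ. Hospital, flight and paramedic teams may use judgement to narrow a loose list in different ways. Case mix would then vary across exactly the groups that the Comparisons section sets against each other.

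The analysis plan has no safeguard. The Statistical analysis section names a t test, regression and chi-square, but no shock-defined analysis set and no covariates. The only pre-defined subgroup is traumatic brain injury.

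**Working it through.** **1. What the list admits.** Write
- X: none of the exclusions other than time applies (so the patient is an adult);
- W: no more than three hours since injury;
- B: blunt or penetrating injury;
- S: at least one of the other listed items is met.

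The exclusion imposes W on everyone. Under *any*, the eligible set is X and W and (B or S). Given W, every patient with B already qualifies, so S matters only for a patient whose injury counts as neither blunt nor penetrating. The Analysis Measures section lists amputation as its own mechanism, so that remainder may not be empty. This is why the other items are almost, and not wholly, redundant. A patient with B but not S is eligible and lies outside the population of the Research Project and Purpose sections.

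**2. The plan's own figure.** The Statistical analysis section derives 200 per group from 0.95 confidence and a 10% margin. With a proportion of 0.5:
- one proportion: 1.96² × 0.25 / 0.10² = 96.04, so 97;
- difference of two proportions: 2 × 96.04 = 192.07 (with unrounded z), so 193 per group.

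Neither gives 200 exactly. Rounding 193 up is a plausible source, and 200 per group gives a half-width of 1.96 × √(0.5/200) = 9.8 points. The documents give no mortality rate, power or share of non-bleeding patients, so the figure cannot show how much dilution the study could bear.

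**3. Dilution.** Let f be the share of non-bleeding patients, equal in both groups and unaffected by TXA, and Δ the absolute effect in bleeding patients. The group-level effect is (1 − f)Δ + f × 0 = (1 − f)Δ. This is 0.75Δ, 0.50Δ and 0.25Δ at f = 25%, 50% and 75%.

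**4. Illustration at 200 per group.** All rates here are assumptions: mortality of 20% versus 10% in shock patients, 2% in non-bleeding patients in both groups, two-sided alpha 0.05. Power is Φ{[|p₁ − p₂|√n − 1.96√(2p̄(1 − p̄))] / √(p₁(1 − p₁) + p₂(1 − p₂))}.

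| f | Mortality, comparator | Mortality, TXA | Difference | Power, n = 200 | n per group for 80% power |
|---|---|---|---|---|---|
| 0 | 20.0% | 10.0% | 10.0 | 80.2% | 199 |
| 25% | 15.5% | 8.0% | 7.5 | 64.5% | 289 |
| 50% | 11.0% | 6.0% | 5.0 | 43.3% | 488 |
| 75% | 6.5% | 4.0% | 2.5 | 20.0% | 1,249 |

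For f = 50%: (0.05 × 14.142 − 1.96 × 0.3944) / 0.3928 = −0.168, and Φ(−0.168) = 0.433.

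Range at f = 50%, with the same 10-point effect in shock patients:
- shock mortality 15%: power falls from 91.8% to 55.8%;
- shock mortality 30%: power falls from 63.8% to 30.9%;
- shock mortality 20%, with non-bleeding patients also at 20%: power falls from 80.2% to 25.9%.

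**5. Unequal shares.** With the same assumed 20% and 2% and no treatment effect at all, shares of 25% and 50% in two groups give mortality of 15.5% and 11.0%. That is a difference of 4.5 points from case mix alone.

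**The case against.** The strongest reply is that eligibility is not enrolment. The protocol says only that TXA use should be considered. The Comparisons and Consent sections place the drug within a massive transfusion protocol for traumatic hemorrhagic shock. Clinicians may therefore treat only patients who are bleeding. A figure that follows the list is not shown and might clarify the intent. This stands in part: a reader might infer that non-bleeding patients will enter every group, and the documents do not show that. It does not remove the contradiction, because the Comparisons section says that patients who fulfil the criteria are given TXA, and the printed list is unambiguous.

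Three further inferences go too far.
- *The second dose becomes automatic.* The Comparisons section calls for re-assessment for hemorrhagic shock on arrival. The test it then states is the same list, so the wording is inconsistent, but the step is not empty.
- *The list alone selects Group D.* Similarity in injury severity and hemodynamics is also required. That makes Group D mirror the treated groups and does not itself require shock.
- *The cited 1.5-point mortality reduction can be multiplied by the share in shock.* The Background reports it as an all-cause result of a 20,000-patient trial, mainly of blunt trauma, and does not call it a shock-only effect. It also compares TXA with no TXA, whereas three of the four listed comparisons are between TXA groups. A reduction of that size would be out of reach anyway: with assumed baseline mortality of 15% to 30%, power at 200 per group is 5% to 6% with no dilution at all.

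**Conclusion.** The inclusion rule is wrong as written. Taken literally, it makes nearly every non-excluded adult with blunt or penetrating trauma eligible. This contradicts the population in the Research Project and Purpose sections, and it makes a qualifying item out of a time window that the Exclusion criteria apply to everyone. That conclusion rests on the text alone.

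The practical size cannot be fixed from the documents. The loss of absolute effect is proportional to the share of non-bleeding patients, provided that TXA does nothing for them and the share is equal across groups. The power figures rest on assumed mortality rates and shares and show direction and scale only. Case-mix differences between teams are a possibility and not an established fact. The point is still worth correcting before patients are enrolled under the rule, because eligibility fixes the population for every outcome.

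**What to change.** The sponsor should reconcile the Research Project, Purpose, Comparisons, Inclusion criteria and Exclusion criteria sections. The protocol should state explicitly whether the three-hour window is a condition on every patient or a criterion that qualifies a patient by itself, so that the eligible population is the one the Purpose names. The reference to the inclusion criteria at the second dose should be made consistent with the re-assessment for shock described beside it. Group D should be selected by the same clarified rule, alongside the similarity requirement in the Design section. If the figure after the list bears on eligibility, it should agree with the text. The clinical criteria themselves are for the investigators.

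The cost is a short protocol edit and a reminder to the crews. Enrolment may be slower if fewer patients qualify.
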